#### 10.6.4. Safety

Extent of Exposure
Run-in Exposure, Treatment Exposure and Post-Treatment On-Study Duration

 
Treatment exposure is calculated separately for run-in open label FF 100mcg, randomized double-blind treatment (Placebo, UMEC 31.25mcg or UMEC 62.5mcg) and open label FF100mcg treatment during the treatment period.
 
Duration of run-in exposure to open label FF100mcg is calculated as: 
 
Run-in stop date – run-in start date + 1
 
 
 
Duration of treatment exposure to study treatment is calculated as: 
 
treatment stop date – treatment start date +1
 
 
 
Duration of Post-treatment time spent on study is calculated as: 
 
Last Scheduled Clinic Visit (i.e., Visit 5 (EOS Visit) or Early Withdrawal Visit) – treatment stop date.
 
 
 

Treatment Exposure Categories

 
Duration of Treatment Exposure during the double-blind treatment period will be summarized for the following categories: 
 
Exposure intervals (weeks): <math>\geq 1</math> day, <math>\geq 4</math> weeks, <math>\geq 8</math> weeks, <math>\geq 12</math> weeks, <math>\geq 16</math> weeks, <math>\geq 20</math> weeks, <math>\geq 24</math> weeks. The category 24 weeks (-5/+2 days) will also be displayed to give the number of participants completing the study per protocol.
 
 
 

Post-treatment On-Study Duration

 
Post-treatment On-Study duration will be summarized for the following categories: 
 
Duration intervals 0 weeks, <math>>0</math> to 4 weeks, <math>>4</math> to 12 weeks, <math>>12</math> weeks.
 
 
 

Adverse Events
Adverse Event Rate

 
Event rate per thousand person-years will be displayed for most On-Treatment AE data in separate tables as listed in Section 10.9.8. Event rate per thousand person-years will be calculated as the number of events x 1000 divided by the total participant exposure during the time-period of interest.
 

AE's of Special Interest

Adverse events of special interest have been defined as AEs which have specified areas of interest for one or more of the treatment groups (FF and/or UMEC). These consist in groupings of preferred terms based on the MedDRA dictionary version used in each reporting effort. Subgroups may be defined, based on relevant combination of preferred terms, or on Standardized MedDRA queries (SMQ).
 
Table 6 (Section 8.3) presents the special interest AE groups for FF and UMEC, defined upon the release of version 20.1 of the MedDRA dictionary.

Pneumonia (AESI)
Pneumonia Event Rate

 
Pneumonia events will be events classified in the pneumonia AESI group (rather than events
 

Pneumonia (AESI)
Pneumonia Event Rate

recorded on the Pneumonia Details eCRF page).
 
 
• Pneumonia event rate will be calculated as the number of events x 1000 divided by the total participant exposure during the time period of interest.
 

Association of Chest X-Ray with Pneumonia Event

 
• A chest X-ray is considered associated with pneumonia if it is performed within -7 to +14 days of the date of onset of pneumonia. Pneumonia is considered to be supported by a chest X-ray if the finding of the associated X-ray is consistent with the diagnosis of pneumonia, as recorded on eCRF page for chest X-ray.
 

MACE	
Broad MACE criteria	Narrow MACE criteria
Ischaemic heart disease SMQ: 
 
• Myocardial infarction SMQ (including fatalities)
 
• Other ischemic heart disease SMQ (including fatalities)
 
	-Myocardial infarction PT -Acute myocardial infarction PT
Central nervous system haemorrhages and cerebrovascular conditions SMQ (including fatalities)	

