## 8.1. Extent of Exposure

Exposure will be summarized for the ITT population.

Exposure to open label FF 100mcg during the run-in period will be summarized and presented in the following categories:  $\geq 1$  day,  $\geq 1$  week,  $\geq 2$  weeks.

Overall extent of exposure to open label FF 100mcg and to double blind study treatment during the randomized treatment period will be summarized in increments of 4 weeks for  $\geq 1$  day,  $\geq 4$  weeks,  $\geq 8$  weeks,  $\geq 12$  weeks,  $\geq 16$  weeks,  $\geq 20$  weeks,  $\geq 24$  weeks. The category 24 weeks (-5/+2 days) will also be presented to capture the number of participants completing treatment per protocol, including permitted visit windows.

Post-treatment duration in study will also be summarized using the categories 0 weeks (i.e. participants who discontinued IP and withdrew from the study at the same time),  $>0$  to 4 weeks,  $>4$  to 12 weeks and  $>12$  weeks for participants who prematurely discontinued from study treatment. The number of days of post-treatment data will also be summarized for all participants with at least one day of post-treatment data.

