- r) Following completion of the pre-dose spirometry assessments, the reversibility test will be conducted between 20 and 60 minutes following 4 inhalations of albuterol/salbutamol or ipratropium aerosol. If airway reversibility is not demonstrated at Visit 1 then the assessment may be repeated within 7 days of Visit 1 (see Section 9.4.3 of the protocol. for details of the criteria to be met before a repeat of the reversibility assessment is permitted). If airway reversibility is successfully demonstrated at the second attempt and all other eligibility criteria assessed at Visit 1 are met then the participant may enter the 2-week run-in period.
- s) Pre-dose spirometry should be performed between 6am and 11am after withholding rescue medication for at least 6 hours and prior to taking the morning dose of study treatment and FF 100 mcg. After V2 pre-dose spirometry assessments should be performed within  $\pm$  1 hour of the V2 spirometry.
- t) Post-dose spirometry is to be performed 3 hours ( $\pm$  15 minutes) after taking the morning dose of study treatment. Rescue medication should be withheld for at least 6 hours prior to the pre-dose spirometry assessments until after completion of the 3-hour post-dose spirometry assessments. Pre- and post-dose spirometry assessments should be performed within  $\pm$  1 hour of the V2 spirometry.

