## 10.4. Appendix 4: Study Phases

### 10.4.1. Study Phases

Study phases for assessments scheduled at a set time will be defined according to the planned relative time of the assessment.

Any events/assessments for participants not in the ITT population will be assigned a Pre-treatment phase.

For all events and assessments, the study phases will be defined as follows:

Study Phase	Definition
Screening/Run-In period	Visit 1 date ≤ Assessment Date/Time < Date of randomization or randomized treatment start date, whichever is later.
On-Treatment during the Study	Randomized Treatment Start Date ≤ Event Onset Date or Assessment Date/Time ≤ Study Treatment Stop Date +1 day or any assessment with a missing or partial date unless there is evidence it was not on-treatment
Post-Treatment during the Study*	Randomized Treatment Stop Date +1 < Event Onset Date or Assessment Date/Time ≤ Last Scheduled Clinic Visit (i.e., Visit 5 (EOS Visit) or Early Withdrawal [EW] Visit) Note: if any participant does not receive a dose of randomized treatment then all post baseline data prior to early withdrawal or EOS visit is considered as post-treatment.
Post-Study	Event Onset Date > Last Scheduled Clinic Visit (i.e., Visit 5 (EOS Visit) or Early Withdrawal Visit) +1 day Note, for participants who continue in the study after IP discontinuation (i.e. where treatment discontinuation date < Visit 5 (EOS visit) date or EW visit date), the rule will be: Event Onset Date > Last Scheduled Clinic Visit (i.e. Visit 5 (EOS Visit) or EW Visit)

\*Only applicable for participants who continue in the study after IP discontinuation

Classification of a concomitant medication into study phases (pre-study period [at study entry], screening/run-in period, on-treatment during the study, post-treatment during the study, or post-study) will be made with reference to the study phase as defined above. A medication will be classified into every period in which it was taken. For medications with partial start and stop dates, the medication will be classified into every period in which it could have been taken.

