

A participant is considered to have completed the treatment period if the answer to the question "Was the study treatment stopped permanently before the scheduled end of the treatment period?" on the Study Treatment Discontinuation eCRF page is "No". Date of completion of treatment period will be the treatment stop date.

A participant is considered to have completed the study if the answer to the question "Was the subject withdrawn from the study?" on the Study Conclusion eCRF page is "No". Otherwise, if the answer is "Yes" then the participant is considered to have withdrawn early from study. The date of study completion/withdrawal as entered on the eCRF will be used as the study completion/withdrawal date.

If a participant prematurely discontinues IP, according to the CRF instructions participants should be reported as continuing in the study if they attend either normal visits, or the safety follow-up visit after the early withdrawal visit (DSCONT='Y'). To identify participants who are continuing in the study per the normal visit schedule and providing post-treatment data, the following will be implemented:

If a participant prematurely discontinues IP and study at the same time, they are not considered to be continuing in the study (i.e. DSCONT will be "N").

If a participant prematurely discontinues IP and only has an EW visit and a safety follow up visit on or after the date of IP discontinuation they are not considered to be continuing in the study (DSCONT will be "Y"). Note, if a participant initially continues in the study following IP discontinuation but then discontinues study prior to the next scheduled clinic visit they will be considered as not continuing in the study as they will not be providing post-treatment data.

If a participant prematurely discontinues IP and has a scheduled visit (not EW or safety follow-up visit) on or after the date of IP discontinuation then the participant is continuing in the study (DSCONT will be "Y").

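### The post-treatment duration formula in SAP 10.6.4 does not yield the 0-week category that SAP 8.1 defines for participants who stop drug and leave the study together

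*SAP*

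**What the plan says.** Four places in the SAP bear on this.

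- **Section 10.6.4 (Safety, extent of exposure).** Post-treatment time on study is the date of the last scheduled clinic visit (Visit 5 or Early Withdrawal) less the stop date: "or Early Withdrawal Visit) – treatment stop date". No other condition is attached.
- **Section 8.1 (Extent of Exposure).** Among participants who stop study treatment early, the lowest category is "0 weeks (i.e. participants who discontinued IP and withdrew from the study at the same time". It is followed by >0 to 4, >4 to 12 and >12 weeks. The section adds: "The number of days of post-treatment data will also be summarized for all participants with at least one day of post-treatment data".
- **Section 10.4.1 (Study Phases).** The on-treatment phase includes the day after the stop date. The post-treatment phase begins later: "Randomized Treatment Stop Date +1 < Event Onset Date or Assessment Date/Time". Its footnote reads: "Only applicable for participants who continue in the study after IP discontinuation".
- **Section 10.6.1 (General).** "If a participant prematurely discontinues IP and study at the same time, they are not considered to be continuing in the study". A participant who "only has an EW visit and a safety follow up visit on or after the date of IP discontinuation" is also described as not continuing, although the flag printed beside that rule is DSCONT = Y. Someone who at first continues but leaves before the next scheduled visit is likewise not continuing, because no post-treatment data will come from them.

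**The concern.** Section 8.1 defines the 0-week row by type of participant, whereas Section 10.6.4 defines it by a date difference. The two agree only if every simultaneous leaver attends the Early Withdrawal visit on the treatment stop date.

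A gap of a day or more is plausible. The schedule in 10.2.1 marks no administration of double-blind treatment at the Early Withdrawal visit, and clinic spirometry is done "prior to taking the morning dose of study treatment and FF 100 mcg". Someone who decides to stop and leave may therefore have taken the last dose the day before. Programmed as written, the formula counts that person as having been followed off treatment.

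What is at stake is the description of follow-up after stopping drug in Table 3.3 and Listing 15. The primary analysis uses a treatment-policy strategy and assumes the remaining missing data are missing at random, so readers will want to know how many early stoppers were actually followed. Table 3.3 could show more of them than there were. It could also disagree with Table 1.3, which reports on- or post-treatment status at each visit.

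**Working it through.** The SAP gives no figure for this point, so there is none to reproduce. The check applies the 10.6.4 formula to a range of gaps and compares the result with the other sections.

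**Step 1. One simultaneous leaver.** Let *g* be the days from treatment stop date to Early Withdrawal visit. The 10.6.4 duration equals *g*.

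| g (days) | Row under 10.6.4 | Phase of the visit by the 10.4.1 dates | Row under 8.1 |
|---|---|---|---|
| 0 | 0 weeks | on-treatment | 0 weeks |
| 1 | >0 to 4 weeks | on-treatment (stop + 1 day) | 0 weeks |
| 2 to 28 | >0 to 4 weeks | post-treatment by date, but the footnote limits that phase to those who continue | 0 weeks |
| 29 | >4 to 12 weeks | as above | 0 weeks |

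The formula matches 8.1 only at *g* = 0. At *g* = 1 it also contradicts the date boundary in 10.4.1. From *g* = 2 it contradicts the footnote and the continuation rule in 10.6.1. If the count of days of post-treatment data is taken from the same duration, which 8.1 does not state, every leaver with *g* of at least 1 enters that summary too.

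**Step 2. Effect on the table (illustration).** The SAP gives neither the number of early stoppers, nor the share who leave at the same time, nor the distribution of *g*. All three are assumed.

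- Randomized total from Section 5.4: 174 + 69 + 21 + 114 + 58 = 436.
- Assume 10% stop early: 0.10 × 436 = 43.6, about 44.
- Assume 60% of these leave at the same time: 0.60 × 44 = 26.4, about 26. Truly followed off treatment: 44 − 26 = 18.
- Let *h* be the share of the 26 with *g* of at least 1. Apparent number followed = 18 + 26*h*.

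| h | Apparent number followed | In the 0-week row |
|---|---|---|
| 0 | 18/44 (41%) | 26 |
| 0.5 | 31/44 (70%) | 13 |
| 1 | 44/44 (100%) | 0 |

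The true figure is 18/44 in every row.

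**Step 3. Other shares.** If a fraction *f* of early stoppers leave at the same time, the true share followed is 1 − *f* and the apparent share is (1 − *f*) + *f h*.

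- *f* = 50% (true 50%): apparent 50%, 62.5%, 75% and 100% for *h* = 0, 25%, 50% and 100%.
- *f* = 80% (true 20%): apparent 20%, 40%, 60% and 100%.

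The size of the distortion is therefore governed by *h*, which the document does not fix.

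**The case against.** **The formula is coherent in itself.** Exposure (stop − start + 1) plus post-treatment time (last visit − stop) equals last visit − start + 1, so each study day is counted once. The extra day in 10.4.1 is a window for assigning events to phases and does not extend exposure. This stands as arithmetic. But the categories in 8.1 are meant to separate people who were followed from people who were not, and the formula does not do that.

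**The gap may be zero.** Section 8.6.2 and schedule note i place ECGs after study treatment at the Early Withdrawal visit, the schedule lists post-dose spirometry there, and 10.6.3 defines a post-dose FEV1 at that visit. A dose that day gives *g* = 0. Section 10.7.2.1 imputes a missing stop date as the Early Withdrawal date, again giving 0. Reading the treatment stop date as the last-dose date is itself an inference. All of this stands. The dosing row of the schedule and these passages disagree about the visit and must be reconciled, and the usual gap cannot be established. A reader might infer that nearly every simultaneous leaver is misplaced and the 0-week row is almost empty, but that is only the *h* = 1 extreme.

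**The governing rules are elsewhere.** A programmer who applies 10.6.1 and the 10.4.1 footnote would place these participants correctly. That is true, but 10.6.4 refers to neither, and followed literally it gives a different answer.

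**Other displays show off-treatment data.** Table 1.3 gives treatment status by visit, Table 2.4 summarizes FEV1 by treatment status, and 7.1.5.1 splits baseline FEV1 by on-treatment, post-treatment or missing value at Week 24. This stands and limits the consequence.

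**Conclusion.** The inconsistency is real but minor. The 10.6.4 formula does not implement the 0-week category of 8.1, nor the rules in 10.4.1 and 10.6.1 on who has post-treatment data. Any simultaneous leaver whose Early Withdrawal visit is at least one day after the stop date is placed above 0 weeks in Table 3.3 (in >0 to 4 weeks for gaps up to 28 days). That person may also be counted as having at least one day of post-treatment data.

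The number affected cannot be determined from the SAP. The range of 18/44 to 44/44 against a true 18/44 rests on the assumed 10% and 60% and on the full span of possible gaps. At the lower end there is no distortion.

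A reader might go further and infer that the retention supporting the primary treatment-policy result is overstated. The SAP does not support this. The primary model uses FEV1 values by visit (7.1.4, 7.1.5.1) and the duration enters no efficacy analysis, so no estimate, interval or p-value changes.

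**What to change.** In Section 10.6.4:

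1. Apply the continuation rule of 10.6.1 first. Participants who stopped drug and left together, or who have only Early Withdrawal or safety follow-up visits after stopping, are not continuing and go to 0 weeks whatever the gap. The label in 8.1 names only simultaneous leavers, so widen it to match.
2. For those who continue, count post-treatment days from the 10.4.1 boundary, that is, after the stop date plus one day.
3. Derive both the 0-week row and the set with at least one day of post-treatment data from that value, and say so in 8.1.
4. In 10.6.1, reconcile the sub-rule that calls a participant not continuing but sets DSCONT to Y.

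Subtracting one day from the present formula is not enough. It gives max(0, *g* − 1), which is 0 at *g* = 1 but still 1 at *g* = 2 and 27 at *g* = 28, so it repairs only a gap of exactly one day.

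The cost is one changed derivation and matching text edits. The day after the stop date will fall in neither the exposure nor the post-treatment duration, which a footnote to Table 3.3 can state. Reported off-treatment follow-up may look less favourable.

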## 10.7. Appendix 7: Reporting Standards for Missing Data

### 10.7.1. Premature Withdrawals

Element	Reporting Detail
General	
 
Withdrawal from Study Prior to Randomization 
 
Participants who are pre-screening failures, screening failures or run-in failures (see Protocol Section 5.5 for the definitions) will be reported to account for the subject disposition.
 
 
 
Withdrawal from Study Treatment 
 
Randomized participants who withdraw from double-blind study treatment prematurely (for any reason) should, where possible, continue to be followed-up as per protocol until the end of the study, after returning to the appropriate asthma therapy per investigator's discretion. Post-treatment data will be included in the statistical analyses.
 
 
 
Participant study completion (i.e. as specified in the protocol) was defined as 'A participant will be considered to have completed the study when they have completed all phases of the study including pre-screening, screening, run-in, the randomized treatment phase, and safety follow-up.'
 
Withdrawn participants were not replaced in the study.
 
All available data from participants who were withdrawn from the study will be listed and all available planned data will be included in summary tables and figures, unless otherwise specified.
 

### 10.7.2. Handling of Missing Data

Element	Reporting Detail
General	
 
Missing data occurs when any requested data is not provided, leading to blank fields on the collection instrument: 
 
These data will be indicated by the use of a "blank" in participant listing displays. Unless all data for a specific visit are missing in which case the data is excluded from the table.
 
Answers such as "Not applicable" and "Not evaluable" are not considered to be missing data and should be displayed as such.
 
No imputation will be made for any missing numerical data, except in the sensitivity analysis of primary endpoints to assess the impact of missing data on study results. Missing data will generally not be considered in the calculation of percentages (i.e., the denominator will not include participants who have missing data at a given time point).
 
 
 

Spirometry	
 
When spirometry has been performed but the reading was unacceptable, a record in the database will indicate that the spirometry was performed but all data will be missing and will not be included in listings or summary displays.
 

Responder analyses	
 
Participants with a missing baseline will have responder status as missing.
 
Participants with missing data at the analysis timepoint, regardless of treatment status, will be considered as a non-responder.
 

Element	Reporting Detail
	
 
For ACQ/SGRQ/AQLQ, participants that have withdrawn from study prior to the visit in question will be imputed as non-responders at all visits after early withdrawal visit where the assessment was expected to be performed.
 

Treatment compliance	
 
For the run-in phase, if date open-label FF 100 ELLIPTA™ DPI device returned is > randomized treatment start date (or Visit 2 for participants who are not treated) date then compliance is set to missing for that container.
 
If a dose counter start count is missing then it will be assumed to be 30 for the ELLIPTA™ DPI. If any dose counter stop is missing then the number of doses received will be set to missing for that container.
 

#### 10.7.2.1. Handling of Missing and Partial Dates

Element	Reporting Detail
General	
 
Partial dates will be displayed as captured in participant listing displays.
 
Dates which are completely missing will not be imputed, with the exception of the treatment stop date. Details for imputation of the treatment stop date are provided below.
 

Study treatment start and stop date	
 
If the study treatment start date is missing, the Visit 2 (Day 1) date will be used.
 
If overall treatment stop date is missing, it will be imputed as follows: 
 
For participants who attended an Early Withdrawal visit, use the date of the Early Withdrawal visit
 
For participants who attended the last on-treatment visit, use the Visit 5 (End of Study) date
 
For participants who died and did not attend the last on-treatment visit, use the date of death
 
For all other participants, use the last recorded exposure stop date
 
 
 
These rules will apply to both randomized double-blind treatment and open label FF100mcg for the treatment period.
 

Adverse Events	
 
The eCRF allows for the possibility of partial dates (i.e., only month and year) to be recorded for AE start and end dates; that is, the day of the month may be missing. In such a case, the following conventions will be applied for calculating the time to onset and the duration of the event: 
 
Missing Start Day: First of the month will be used unless this is before the start date of study treatment; in this case the study treatment start date will be used and hence the event is considered On-treatment as per Appendix 4: Study Phases
 
Missing Stop Day: Last day of the month will be used.
 
 
 
Completely missing start or end dates will remain missing, with no imputation applied. Consequently, time to onset and duration of such events will be missing.
 

Concomitant Medications/ Medical History	
 
Partial dates for any concomitant medications recorded in the CRF will be imputed using the following convention: 
 
If the partial date is a start date, a '01' will be used for the day and 'Jan' will be used for the month
 
If the partial date is a stop date, a '28/29/30/31' will be used for the day
 
 
 

Element	Reporting Detail
	(dependent on the month and year) and 'Dec' will be used for the month. 

• The recorded partial date will be displayed in listings.

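### A missing treatment stop date becomes the Early Withdrawal visit date even for a participant recorded as having stopped study drug earlier, so off-drug follow-up is counted as exposure and as on-treatment data

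*SAP*

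**What the plan says.** SAP 10.7.2.1 gives an ordered rule for a missing overall stop date:

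- Early Withdrawal (EW) visit: "For participants who attended an Early Withdrawal visit, use the date of the Early Withdrawal visit".
- Visit 5: "For participants who attended the last on-treatment visit, use the Visit 5 (End of Study) date".
- Death before that visit: the date of death.
- Remainder: "For all other participants, use the last recorded exposure stop date".

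For the start date, the same table says "If the study treatment start date is missing, the Visit 2 (Day 1) date will be used". Its general row says "Dates which are completely missing will not be imputed, with the exception of the treatment stop date".

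The plan also expects people to stop study drug and remain in the trial. Sections 2.3 and 10.7.1 encourage continued follow-up. Section 10.6.1 treats treatment discontinuation and study withdrawal as separate events on separate eCRF pages. It counts a participant as continuing if that person "has a scheduled visit (not EW or safety follow-up visit) on or after the date of IP discontinuation".

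The stop date sets the on-treatment phase in 10.4.1, which covers "Event Onset Date or Assessment Date/Time ≤ Study Treatment Stop Date +1 day". It also enters the formulas for exposure and post-treatment duration (10.6.4) and for compliance (10.6.2).

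**The concern.** For a participant followed off drug, the EW visit marks leaving the study. It does not mark the last dose. The EW rule treats the two as one date whether or not an earlier stop is on record, and it outranks the recorded exposure date.

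The consequences follow from the plan's own definitions. The displays exposed are:

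- the supportive on-treatment FEV1 analysis (7.1.5.1);
- the on-treatment vital-sign and ECG models (8.6.4);
- the on-treatment adverse event tables and exposure-adjusted rates (8.2, 10.6.4);
- exposure, compliance and post-treatment duration;
- the Kaplan-Meier curve of time to treatment discontinuation (6.1.1).

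These displays depend on separating on-drug from off-drug time, and early stoppers are the participants for whom that separation matters.

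A smaller problem lies in the start-date rule. It contradicts the general row above it, which allows imputation of the stop date only. It also makes no mention of participants who never took a dose.

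**Working it through.** The SAP states no figure on this point, so there is none to reproduce. The check applies the plan's own date formulas. Stop days and numbers of participants are assumptions.

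**Inputs**
- Exposure = stop − start + 1 (10.6.4).
- Post-treatment duration = last scheduled clinic visit (Visit 5 or EW) − stop (10.6.4).
- On-treatment runs to stop + 1 day (10.4.1).
- Compliance = 100 × doses / (stop − start + 1) (10.6.2).
- Visits at Days 29, 85 and 169 (10.2.1). EW data from Day 127 onward are slotted to Week 24 (10.3).
- Planned arm size 128 (2.3).

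**Step 1: post-treatment duration.** If the stop date is set to the EW date, duration = EW date − EW date = 0 in every case. Section 8.1 defines the 0-week category as stopping drug and study at the same time. A person followed off drug for months is therefore placed in a category that the plan reserves for someone else.

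**Step 2: one participant.** Assume start Day 1, last dose Day 40 with 40 doses taken, EW visit Day 150, overall stop date missing.

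| Quantity | Last dose as stop date | EW rule |
|---|---|---|
| Exposure | 40 − 1 + 1 = 40 days | 150 − 1 + 1 = 150 days |
| Compliance | 40/40 = 100% | 40/150 = 26.7% |
| Post-treatment duration | 150 − 40 = 110 days | 0 days |
| Week 12 FEV1 (Day 85) | after Day 41: post-treatment | by Day 151: on-treatment |
| EW FEV1 (Day 150, slotted to Week 24) | post-treatment | on-treatment |

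**Step 3: range of excess days.** With an assumed last dose on Day 29, an EW visit on Day 85 gives 85 − 29 = 56 excess days. A last visit on Day 169 gives 169 − 29 = 140.

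**Step 4: one arm.** Full exposure is 128 × 169 = 21,632 days, or 59.2 person-years. Inflation = 21,632 / (21,632 − excess) − 1.

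- 1 participant, 56 days: 0.15 person-years, 0.3%.
- 2 participants, 56 to 140 days each: 0.5% to 1.3%.
- 10 participants, 140 days each: 1,400 days, 3.8 person-years, 6.9%.

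The counts randomized in Section 5.4 sum to 174 + 69 + 21 + 114 + 58 = 436, about 145 per arm, so the percentages would be slightly lower in practice. Off-drug events also enter the numerator of the adverse event rate, so the net direction of the change in the rate is not determined.

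**Step 5: start date.** Sections 4 and 10.6.1 exclude an undosed participant from the ITT population only if that person is also recorded as a screen or run-in failure. Other undosed participants stay in. Read literally, the start date becomes Visit 2, and an EW visit on Day 29 then yields 29 − 1 + 1 = 29 days of exposure where 0 is true. Their data are handled differently: the note in 10.4.1 begins "if any participant does not receive a dose of randomized treatment then all post baseline data" and goes on to class those data, up to EW or end of study, as post-treatment. Only the exposure is left open.

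**The case against.** The case against is substantial.

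- The EW rule does harm only when four things coincide: an early stop, continued off-drug follow-up, a later EW visit, and a missing overall stop date. Database cleaning before release (3.1) should make the last of these rare. This stands, and it limits the size of the problem.
- For someone who leaves drug and study together, the EW date is a sensible default. The schedule collects study drug at that visit. This also stands, and the fix keeps the default for those people.
- The last recorded exposure stop date may belong to an earlier container record, so using it could cut true exposure short. This is a real downside of the fix.
- Section 10.6.1 quotes only a yes/no question from the discontinuation page. If that page also holds a date, the date may already supply the overall stop date and the rule would seldom be needed. The SAP does not settle this.

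Four stronger readings are tempting, and the document does not support them:

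- A reader might infer that never-dosed participants' data become on-treatment. Section 10.4.1 says they are post-treatment.
- A reader might infer that the Visit 5 rule has the same defect as the EW rule. Its reference to the last on-treatment visit can be read as excluding people already off drug, in which case they fall to the last recorded exposure date. The wording is ambiguous, and no more than that.
- A reader might infer that the main efficacy result is at risk. The primary analysis (7.1.4) and the exploratory efficacy analyses (7.3.4) use on- and post-treatment data together, so the misclassification does not change which data they include. The secondary endpoint is largely protected, because people off drug were not required to do the 3-hour test (7.2.4).
- A reader might infer that the on-treatment effect is diluted. Stoppers in every arm return to asthma therapy at the investigator's discretion (10.7.1), so the direction is not established.

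**Conclusion.** The point holds for the EW rule. In an identifiable subgroup, the stated rule gives a stop date later than the recorded discontinuation and forces post-treatment duration to 0, in conflict with 8.1 and 10.6.4. This is a wrong rule for those people, which is more than a missing detail.

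Severity is minor. The rule acts only when the stop date is missing, and the SAP does not say how often that happens. The person-time figures rest on assumed numbers of participants and assumed stop days, and nothing in the document supports the top of that range. What is exposed is the supportive on-treatment FEV1 analysis and the safety, exposure, compliance and discontinuation displays.

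The Visit 5 wording needs clarifying. The start-date rule needs reconciling with the general row of its own table and with 10.4.1.

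**What to change.** In 10.7.2.1:

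1. If the overall stop date is missing and the participant is recorded as having stopped treatment before the EW visit or Visit 5, use any recorded discontinuation date. If there is none, use the last recorded exposure stop date.
2. Use the EW or Visit 5 date only for participants not recorded as having stopped earlier, and state that the Visit 5 rule covers only those still on treatment at that visit.
3. Name the field that identifies an earlier stop. The yes/no answer alone cannot separate a participant who stopped at the EW visit from one who stopped months before it.
4. State that participants with no dose get no imputed start date and have zero exposure. Amend the general row so that it agrees with the start-date rule.

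The cost is a wording change and a small edit to one derivation, made before unblinding. No new data should be needed, because the last recorded exposure date is already in the plan. Where that date comes from an earlier record, exposure could be slightly understated. Listing every imputed stop date with its source would let a reader judge this.
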